# 2.2 Safety

All operative site events as well as all serious adverse events (SAEs), excluding elective procedures, will be collected and compared to published data. It is expected that the AE rates reported for the Restoration® ADM X3® Acetabular System will be comparable to those reported in the literature for other primary THR systems and similar dual mobility cups on the market. Details regarding AE definitions, recording and reporting are in Section 8 of this protocol, Adverse Events.

# 3 Clinical Study Plan

# 3.1 Study Design

A prospective, post-market, multi-center design will be employed. Radiographs will be assessed by an independent reviewer.

#### 3.2 Number of Centers

Cases will be enrolled at up to 12 centers. The enrollment goal is 29 cases per center utilizing the Restoration® ADM X3® Acetabular System but will vary dependent upon the number of participating centers. Although a goal is presented, there is no maximum limit to the number of cases that a center may enroll. In the event that a center far exceeds the enrollment goal, Stryker may ask the center to cease enrollment so as not to skew the data. All participating centers will comply with the federal regulations regarding patient informed consent and Institutional Review

Board (IRB) or Ethics Committee (EC) approval. Non-compliance of a study center may result in termination of the center's participation in the study.

# 3.3 Number of Subjects

Cases will be enrolled until a total of 350 cases receive the Restoration® ADM X3® Acetabular System. Additionally, a minimum of 100 cases (within the study population) will receive the Accolade® II Hip Stem.

Stryker will monitor enrollment to ensure the enrollment goals for the Restoration® ADM X3® Acetabular System and the Accolade® II Hip Stem are satisfied.

# 3.4 Estimated Study Duration

The enrollment period is estimated to be a maximum of 24 months; cases will be evaluated as per the evaluation schedule until each case reaches 10 years.

To allow for a learning curve with the use of the device, enrollment of cases into the study will commence when five cases have been completed at the center using the Restoration® ADM X3® Acetabular System.

# 4 Eligibility

The following criteria will be used to distinguish patients eligible for enrollment into this study. Proper implant selection must consider design, fixation, and environmental variables including: patient weight, age, bone quality and size, activity level and pre-operative level of health, as well as the surgeon's experience and familiarity with the device. For patients with poor proximal bone quality, the use of supplemental adjunctive proximal fixation/support is advised for implant stability.

#### 4.1 Inclusion Criteria

- A. Patient has signed an IRB/EC approved, study specific Informed Patient Consent Form.
- B. Patient is a male or non-pregnant female, skeletally mature and age 18-75 years at time of study device implantation.

- C. Patient has a diagnosis of Non-Inflammatory Degenerative Joint Disease (NIDJD).
- D. Patient is a candidate for a primary cementless acetabular replacement.
- E. Patient is willing and able to comply with postoperative scheduled clinical and radiographic evaluations and rehabilitation.

#### 4.2 Exclusion Criteria

- F. Patient has a Body Mass Index (BMI) ≥ 40.
- G. Patient has an active or suspected latent infection in or about the affected hip joint at time of study device implantation.
- H. Patient has a neuromuscular or neurosensory deficiency, which limits the ability to evaluate the safety and efficacy of the device.
- Patient is diagnosed with a systemic disease (e.g. Lupus Erythematosus) or a metabolic disorder (e.g. Paget's disease) leading to progressive bone deterioration.
- J. Patient is immunologically suppressed or receiving steroids in excess of normal physiological requirements (e.g. > 30 days).
- K. Patient requires revision surgery of a previously implanted total hip replacement or hip fusion to the affected joint.
- L. Patient has a known sensitivity to device materials.
- M. Patient is a prisoner.

# **5 Subject Enrollment**

# 5.1 Treatment Assignment

All subjects will receive the Restoration® ADM X3® Acetabular System with a minimum of 100 cases (within the study population) that will receive the Accolade® II Hip Stem.

Stryker will monitor enrollment closely to ensure that the enrollment goals of Restoration® ADM X3® Acetabular System and the Accolade® II Hip Stem are satisfied.

#### 5.2 Randomization

The study will enroll under a non-randomized study design.

# **6 Device Description**

# 6.1 Study Device

The Restoration® ADM X3® Acetabular System and the Accolade® II Hip Stem have been cleared for use in the United States; therefore, this study is considered a post-market assessment. All cases in this study will receive the Restoration® ADM X3® Acetabular System which consists of two components, an acetabular cup and an X3® UHMWPE acetabular insert.

Additionally, only the following **Stryker compatible** ancillary devices may be used, according to this study protocol:

- o Compatible Stryker femoral stem (minimum of 100 Accolade® II Hip Stems)
- 28 mm Stryker femoral head\*

The acetabular cup is manufactured from wrought cobalt chromium alloy with a CP Titanium and HA coating and is intended for cementless use. The inner surface of the cup is highly polished. The outer geometry of the Restoration® ADM Acetabular Shell is based on Stryker's Trident® Acetabular Shell and has a PSL® design. The rim of the Restoration® ADM Acetabular Shell has an anatomic cut-out to prevent conflict with the ilio-psoas muscle.

The Restoration® ADM X3® Acetabular Insert is composed of Stryker Orthopaedics sequentially annealed UHMWPE, X3®. The ID is compatible with a 28 mm Stryker femoral bearing head only. \*The Restoration® ADM Acetabular Shell is not intended for use with the Stryker LFIT™ Anatomic CoCr femoral bearing head larger than 28mm.

The Restoration® ADM X3® Acetabular Shell is available in left and right configurations ranging in sizes 46 mm – 64 mm OD which are coupled with the polyethylene inserts ranging in sizes 40 mm - 58 mm OD. There is a 6 mm difference between cups and inserts and inserts are available in 0 degrees only.

The catalog numbers for the Restoration® ADM Acetabular Shell, permissible according to this study protocol are in the following format, where 'XXX' varies by size:

1235-2-XX1 (Right) 1235-2-XX2 (Left) The catalog numbers for the Restoration® ADM X3® Acetabular Insert, permissible according to this study protocol are in the following format, where 'XX' varies by size:

1236-2-8XX

Table 2. Restoration® ADM X3® Acetabular System Shell/Insert Thickness/Head Compatibility

Restoration ®	Restoration ®	Insert	Femoral Head
ADM Shell	ADM X3 ® Insert	Thickness	Diameter
(OD/mm)	(OD/mm)	(mm)	(mm)
46	40	5.9	28
48	42	6.9	28
50	44	7.9	28
52	46	8.9	28
54	48	9.9	28
56	50	10.9	28
58	52	11.9	28
60	54	12.9	28
62	56	13.9	28
64	58	14.9	28

The patentedb sequential irradiation and annealing manufacturing process for X3® offers increased wear resistance and virtually eliminates free radicalsc while preserving mechanical

<sup>b U.S. Patent # 6,174,934 6,372,814 6,664,308 6,818,020 7,517,919

 $^{\rm c}$  X3 UHMWPE virtually eliminates free radicals, as measured by Electron Spin Resonance (ESR). A very low (noise level, near instrument detection limit) concentration of residual free radicals was detected in the X3 UHMWPE. A 99% reduction of free radicals (14  $\pm$  2 x 10^14 spins/gram versus 1550  $\pm$  32 x 10^14 spins/gram) was found when compared to N2Vac gamma sterilized UHMWPE.

propertiesd,e,f,g. X3® is irradiated by 3 MRads gamma radiation and annealed (heated below melting temperature) three times for a total cumulative dose of 9 MRads.

The Accolade® II Hip Stem will be available in 12 sizes ranging from size 0 through 11. Stem length will range from 93 mm to 126 mm in 3 mm increments. The neck lengths of the Accolade® II Hip Stem range from 27 mm to 40 mm and are proportional relative to the different body geometry. Additionally, the necks are available in two angles (127° and 132°) that provide dual offsets.

For subjects implanted with the Accolade® II Hip Stem, the following catalog numbers are permissible according to this study protocol and are in the following format, where 'XXXX' varies by size:

6720-XXXX 6721-XXXX

#### 6.2 Device Retrieval Process

Stryker Orthopaedics will retrieve any Restoration® ADM X3® Acetabular System components and the Accolade® II Hip Stem (when applicable) and/or adjacent tissues for analysis to help characterize potential device-related complications. In the event that any portion of the Restoration® ADM X3® Acetabular System or the Accolade® II Hip Stem is removed from a study subject, the procedure outlined in the Retrieval Analysis Protocol (Appendix B) should be followed. In addition:

 $^{m d}$  X3 UHMWPE maintains mechanical properties after accelerated oxidative aging. No statistical difference was found for Tensile Yield Strength, Ultimate Tensile Strength and Elongation as measured per ASTM D638 before and after exposure to ASTM F2003 accelerated aging (5 Atmospheres (ATM) of oxygen at 70°C for 14 days). Tensile Yield Strength was 23.5  $\pm$  0.3 MPa and 23.6  $\pm$  0.2 MPa, Ultimate Tensile Strength was 56.7  $\pm$  2.1 MPa and 56.3  $\pm$  2.3 MPa and Elongation was 267  $\pm$  7% and 266  $\pm$  9% before and after accelerated oxidative aging, respectively.

 $^{\rm c}$  X3 UHMWPE resists the effects of oxidation. No statistical difference was found for Tensile Yield Strength, Ultimate Tensile Strength, Elongation, Crystallinity and Density as measured per ASTM D638, D3417 and D1505 before and after ASTM F2003 accelerated aging (5 ATM of oxygen at 70°C for 14 days). Tensile Yield Strength was 23.5  $\pm$  0.3 MPa and 23.6  $\pm$  0.2 MPa, Ultimate Tensile Strength was 56.7  $\pm$  2.1 MPa and 56.3  $\pm$  2.3 MPa, Elongation was 267  $\pm$  7% and 266  $\pm$  9%, Crystallinity was 61.7  $\pm$  0.6% and 61.0  $\pm$  0.5%, and Density was 939.2  $\pm$  0.1 kg/m3 and 939.2  $\pm$  0.2 kg/m3 before and after accelerated oxidative aging, respectively.

f "Improved Strength of Cross-linked UHMWPE Without Compromising Oxidation/Fatigue Resistance and Wear", Yau SS; Wang A, Lovell T. 2007 Combined ORS Poster #496.

<sup>g "Wear, oxidation and mechanical properties of a sequentially irradiated and annealed UHMWPE in total joint replacement", A.Wang, H.Zeng, S-S Yau, A. Essner, M. Manley and J. Dumbleton, Journal of Physics, D:Appl: Phys 39 (2006).

- 1. When revision of a study subject is scheduled, the study coordinator (SC) should contact the Clinical Study Manager (CSM) or Clinical Study Associate (CSA) assigned to the project, as soon as possible.
- The CSM or CSA will send a retrieval container to the SC.
- 3. After the device is explanted, the SC or an identified Stryker field representative will retrieve the device and place it in the retrieval container, following the instructions in Appendix B.
- 4. The SC, an identified field representative or the CSM/CSA will complete a Product Experience Report (PER).
- 5. If not completed by the CSM or CSA, the PER should be faxed to Stryker Product Surveillance at [contact], as well as to Stryker Clinical Research at [contact].
- 6. The PER should be attached to the retrieval container and sent to Product Surveillance.

  A de-identified operative report should be included, when available.
- 7. The CSM or CSA will follow up with Product Surveillance to obtain a PER number.
- 8. A summary of results will be provided to the investigator upon his/her request.

# 7 Evaluations

# 7.1 Preoperative Visit

During the preoperative visit, patients that are possible candidates for this study will be screened to determine if they meet the inclusion/exclusion criteria. If the patient is a candidate, the investigator will propose participation in the study to the patient, according to GCP guidelines. Patients must sign an IRB/EC approved Informed Patient Consent Form prior to participating in any study related activities. Consent must be obtained within 4 months prior to surgery.

Once the patient has been consented, preoperative data will be collected including: demographics, medical history, HHS, SF-12, LEAS, EQ-5D, AP pelvis, AP femur and lateral radiographs.

All preoperative data must be collected within 4 months prior to the scheduled date of surgery, with the exception of radiographs, acceptable within 1 year prior to the scheduled date of surgery. All information collected preoperatively will be used to quantify the sample population and compare postoperative progress.

# 7.2 Surgery

Surgical details will be collected from the operative notes and at the time of surgery.

#### 7.3 6-week Visit

During the 6-week visit (± 3 weeks), the following evaluations will be collected: HHS, SF-12, LEAS, EQ-5D, AP pelvis, AP femur and lateral radiographs.

### 7.4 Annual Follow-up Visits

Clinical data will be collected via office visit by the investigator at the following annual postoperative intervals: 1-year, 2-year, 3-year, 4-year and 5-year. Tools for postoperative evaluation will be the HHS, AP pelvis, AP femur and lateral radiographs. Radiographs will also be obtained at 1 year and then annually to 5 years postoperatively.

Patient outcomes data will also be collected with the required SF-12, LEAS, and EQ-5D patient questionnaires at each annual visit at the 1-year through 5-year follow-up visits.

All clinical data, radiographs, and patient outcomes data must be collected within  $\pm$  2 months of the 1-year and 2-year anniversary dates. For remaining annual time points, the window expands to  $\pm$  3 months of the 3-year anniversary date and  $\pm$  4 months of the 4-year through 10-year anniversary dates.

The initial phase of the study will continue for 5 years after surgery and include collection of the previously described radiographs, HHS, SF-12, LEAS and EQ-5D patient questionnaires. In the second phase of the study, all subjects will complete a brief Follow-up Questionnaire annually at the 6-year, 7-year, 8-year, 9-year and 10-year follow-up intervals. This form may be completed by the SC during a subject telephone interview, or by the subject either at home or during a clinic visit. The questionnaire will be used to obtain the following information, at a minimum:

- Subject satisfaction with the hip replacement
- Presence of any pain in the study hip
- Any surgeries performed on the study hip
- Any dislocations in the study hip

The questionnaire will also provide information on any revisions and enable calculation of the Kaplan-Meier Survival Curve necessary to meet the primary endpoint of the study.

Additionally, at investigational sites that choose to continue collecting clinical and radiographic data during the second phase of the study, subjects will be evaluated again at 7 and 10 years after surgery.

# **8 Adverse Events**

### 8.1 Reporting of Adverse Events

The AE reporting requirements for this study are as follows:

- All AEs that meet the definition of serious, excluding elective procedures
- All AEs related to the operative site, regardless of seriousness

Elective procedures meeting the definition of an SAE do not need to be reported as AEs according to this study protocol. Examples of such elective procedures include, but **are not limited to**, the following commonly seen events:

- Contralateral THR
- Total Knee Replacement
- Rotator Cuff Surgery
- Cataract Surgery

Such events will not be captured on the AE electronic Case Report Form (eCRF) but rather will be captured on the Postoperative Functional Evaluation at the 6-week, 1-year, 2-year, 3-year, 4-year and 5-year time points. Additional events of this nature will be captured on the 7-year and 10-year functional evaluations if the investigator chooses to bring subjects in for these optional visits. On these functional evaluations, investigators and SCs will be prompted to question subjects as to whether they have seen a doctor for any reason, been hospitalized for any reason or have a current impediment to their function.

Additionally, SCs will be responsible for following up with the subjects regarding any questionable responses received on the Follow-up Questionnaire administered in postoperative years 6 through 10. If it is determined upon this further investigation that a protocol-defined AE has

Restoration® ADM X3® Study with Long Te Stryker Orthopaedics Clinical Study Protoc Version 3.0	erm Data Collection for the Accolade ® II Hip Stem col	Page 30
occurred, the SC will be responsib	le for completing an AE eCRF, submitting the e	event to Stryker
and reporting to the IRB, as require	ed.	

The following decision tree facilitates identification of AEs for which reporting is required under this study protocol:

Start Site becomes aware of Adverse Event Is the event related to the Does the AE meet the Do NOT report to No-No→ operative site? criteria for Seriousness? Stryker Yes Yes Report AE to Stryker via AE Is the event an Yes-Form elective surgery? No Report AE to Stryker via AE Form End

Figure 4. Adverse Event Decision Tree

CONFIDENTIAL

This material is the property of Stryker Orthopaedics. Do not disclose or use except as authorized in writing by Stryker.

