### Adverse Event Reporting Period

The study period during which AEs must be reported is normally defined as the period from the initiation of any study procedures to the end of the study treatment follow-up. The start of study procedures is considered to be the point of consent. Any AEs which fit the protocol defined reportable events must be reported from the time of consent until study completion.

At each contact with the subject the investigator must seek information on AEs by specific questioning and, as appropriate, by examination. Information on protocol defined AEs should be recorded immediately in the source document and also in the appropriate AE module of the eCRF. All clearly related signs, symptoms and abnormal diagnostic procedure results should be recorded in the source document and grouped under one diagnosis, as appropriate. The clinical course of each event should be followed until resolution or until it is determined at the end of the study that the AE will not resolve.

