#### Serious Adverse Event

A **SAE** meets one or more of the following definitions:

- Resulted in in-patient hospitalization
- Resulted in prolonged existing hospitalization
- Resulted in persistent or significant disability/incapacity
- Resulted in permanent impairment of a body function or permanent damage to a body structure
- Necessitated medical or surgical intervention to preclude permanent impairment of a body function or permanent damage to a body structure
- Was a life-threatening situation
- Resulted in patient death

Elective procedures meeting the definition of an SAE do not need to be reported as AEs according to this study protocol.

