## Restoration®ADM X3®Acetabular System POST-OP FUNCTIONAL EVALUATION

| IV. EVENTS                                                               |                                                                           |                          |        |                                         |  |  |  |  |  |  |
|--------------------------------------------------------------------------|---------------------------------------------------------------------------|--------------------------|--------|-----------------------------------------|--|--|--|--|--|--|
| K. Have there been any protocol                                   | defined Adverse Events sin                                                | nce the last visit?      | Yes*   | ○ No
ete an AE form for each. |  |  |  |  |  |  |
| USE THIS SECTION TO REPORT M                                             | EDICAL EVENTS OTHER THA                                            | N PROTOCOL DEFINE        |        |                                         |  |  |  |  |  |  |
| L. Has the subject seen a doctor                                         | Has the subject seen a doctor for any medical event since the last visit? |                          |        |                                         |  |  |  |  |  |  |
| *If Yes, specify:                                                        |                                                                           |                          |        |                                         |  |  |  |  |  |  |
|                                                                          |                                                                           |                          |        |                                         |  |  |  |  |  |  |
| M. Has the subject been hospita  *If Yes, specify (check all that apply) | lized for any elective surge                                              | ry since the last visit? | ○ Yes* | ○ No                                    |  |  |  |  |  |  |
| Contralateral Hip                                                        | Contralateral Knee                                                        | Ipsilateral Knee         | [      | Contralateral Shoulder                  |  |  |  |  |  |  |

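### Section 8.1 promises a question on hospitalisation for any reason, but item M of the draft Post-Op Functional Evaluation asks only about elective surgery, so no item names unplanned admissions

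*Combined protocol and SAP*

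**What the plan says.** Section 8.1 makes two classes of event reportable. One is "All AEs that meet the definition of serious, excluding elective procedures"; the other is any AE at the operative site. Elective procedures are instead to be "captured on the Postoperative Functional Evaluation at the 6-week, 1-year, 2-year, 3-year, 4-year and 5-year time points", and at 7 and 10 years where a site holds those optional visits. The same paragraph closes by saying that these evaluations will prompt staff to ask whether the subject has seen a doctor for any reason, or has "been hospitalized for any reason or have a current impediment to their function".

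Section 8.2 lists "Resulted in in-patient hospitalization" as a criterion that makes an AE serious. Under Adverse Event Reporting Period, at each contact "the investigator must seek information on AEs by specific questioning".

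The Post-Op Functional Evaluation in Appendix F has four event items:

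- Item K ("K. Have there been any protocol", with the rest split across table cells) asks about protocol-defined AEs since the last visit and calls for an AE form for each.
- Item L asks "Has the subject seen a doctor for any medical event since the last visit".
- Item M asks about hospitalisation, but the legible part of the question reads "lized for any elective surge", that is, elective surgery, followed by a checklist of elective operations.
- Item N asks whether anything currently affects function.

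Items L to N stand under a heading that reserves that part of the form for medical events that are not protocol-defined AEs.

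**The concern.** Section 8.1 describes three prompts, and the form delivers two of them. The third has been narrowed to the one category of admission that the protocol exempts from AE reporting. The admissions that must be reported are left without a question that names them.

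What is at stake is the completeness of the SAE count. Section 2.2 collects SAEs and compares them with published data, Section 9.2.2 presents AE rates with 95% confidence intervals, and Section 12.3 compares complication rates with published ones. A missed admission can only lower the study's rate, so incomplete capture would make the device look safer against the literature. A confidence interval does not reflect under-ascertainment.

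**Working it through.** No arithmetic applies; this is a comparison of text. First, each prompt in Section 8.1 against the form:

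| Prompt described in Section 8.1 | Item in Appendix F | Match |
|---|---|---|
| Doctor seen, any reason | L: doctor seen for any medical event | Close |
| Hospitalised, any reason | M: hospitalised for elective surgery | Narrowed |
| Current impediment to function | N: anything affecting function | Yes |

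Second, the path of an unplanned in-patient admission that results from an adverse event:

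1. It meets the seriousness criterion in Section 8.2.
2. It is not an elective procedure, so Section 8.1 makes it reportable, and it is therefore a protocol-defined AE.
3. On the form it belongs under item K. Item K does not mention hospitalisation, so staff must turn the definition into a question the subject can answer.
4. The accurate answer to item M is no, because the admission was not for elective surgery.
5. Item L may bring it to light, since an admission usually involves a doctor. But item L sits under the heading for other events, and the legible text asks only for details, with no branch to an AE form. The Follow-up Questionnaire for years 6 to 10, by contrast, tells the coordinator to review every response for a possible AE.

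Third, the order of the filters. The decision tree in Section 8.1 (Figure 4) establishes seriousness first and only then asks whether the event was elective surgery. Item M applies the elective filter inside the question, before the site has learned that there was an admission.

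The prompt in Section 8.1 is therefore absent from the form. Item K is a real but general prompt for the same events, and item L and the questioning duty are indirect ones.

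**The case against.** The strongest reply is that SAE capture is item K's job and that item K does it. It stands ahead of L to N, is asked at every visit where the form is used, and covers every SAE that is not an elective procedure. It is handled by research staff, for whom applying an SAE definition is routine. Item L, the questioning duty, the requirement in Section 8.4 to record events between visits, and the inpatient-hospitalisation box on the AE form all support it. The prompt sentence in Section 8.1 also closes a paragraph about where elective procedures are recorded, so item M may do what was meant and the looser wording may be in Section 8.1. Finally, Appendix F holds draft specifications (Section 11.1), completion instructions are in a separate guide (Section 11.4), and centres write their own source worksheets (Section 11.3). Any of these could tell staff to ask about hospital stays.

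Much of this stands. A reader might infer that unplanned admissions have no prompt at all in years 0 to 5; item K rules that out. A reader might also infer that elective admissions are never SAEs, or that the study discards them. Sections 8.1 and 8.2 say instead that elective procedures meeting the SAE definition are exempt from AE reporting, and Section 8.1 has them recorded on this form.

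What does not fall away is the contradiction. Whichever text reflects the intent, Section 8.1 states a prompt that the specification lacks, and a general AE item is a weaker aid to recall than a question that names hospital stays.

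**Conclusion.** The point holds in limited form. Section 8.1 and item M disagree, and no item on the form names unplanned hospitalisation. Capture of these reportable SAEs from 6 weeks to 5 years therefore rests mainly on how staff use item K. Any resulting error in the SAE rate would be downward.

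Its size cannot be estimated from the documents. It is tempting to assume, say, that 20% to 40% of subjects have an unplanned admission within 5 years and that 10% to 25% of these go unrecorded, giving an understatement of 0.20 × 0.10 = 2 points to 0.40 × 0.25 = 10 points. Neither range has a source in the documents, and the product gives no credit to item K, item L or the questioning duty. It should not be read as an estimate of the effect of this wording, nor as evidence that a bias exists.

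The consequence is also bounded by the analysis. AE rates are summarised descriptively, with no formal SAE test specified. The primary endpoint is not affected: femoral head dislocation is an operative-site event, reportable whether or not it is serious, and has its own entry on the AE form. The conclusion assumes that the live form follows the draft specification, which should be checked first.

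**What to change.** Reword item M to ask whether the subject has been hospitalised for any reason since the last visit. If the admission was for elective surgery, keep the existing checklist; send any other admission to item K and an AE form. Rewording alone would create a new conflict, because item M sits under a heading that excludes protocol-defined AEs. Either move item M above that heading or amend the heading. Use the revised form at every functional evaluation, including the optional 7- and 10-year visits, and at each subject's first visit under it ask once about the whole time since surgery.

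Section 8.1 then needs no change, since the form would do what it already says. The cost is one eCRF revision with one added branch, and some additional AE forms. No extra visit is needed.
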